8.1.4 FULL TRIAL ANALYSES

Primary analysis: Analysis will be performed by intention to treat. Intention to treat analysis will be supplemented by a sensitivity analysis that excludes subjects who did not complete the allocated treatment plan. Primary outcome event rates will be compared in the experimental and standard of care arm by an unadjusted Fisher's test of proportions, with 95% confidence intervals provided.

Secondary analysis: Analysis will be performed by intention to treat. Intention to treat analysis will be supplemented by a sensitivity analysis that excludes subjects who did not complete the allocated treatment plan. Proportions will be compared between study arms by an unadjusted Fisher's test, with 95% confidence intervals reported. The following outcomes will be analyzed:

symptomatic VTE, symptomatic ATE, major bleeding, CRNMB, non-major non-CRNMB, medication intolerance/reaction, and all-cause mortality.

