4.2 TRIAL DESIGN

TRIM-Line is an open-label, randomized controlled feasibility pilot trial comparing rivaroxaban 10mg po daily vs standard of care (no treatment) in patients with active cancer and indwelling CVC. This will involve 3 centres, Ottawa as the coordinating centre, Halifax and Edmonton.

Cancer patients with insertion of CVC will be eligible.

While the primary outcome is feasibility based clinical data will be collected using the same methodology as the proposed full-sized trial. Should there be no major changes to the trial design based on the findings of this pilot study's feasibility data that would render the collected data inappropriate for inclusion, the clinical data collected during this trial will be included in the primary and secondary analysis for the full trial.

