4.7 RANDOMIZATION

Consenting subjects will be randomized at 1:1 ratio to treatment or non-treatment arms at study enrollment with treatment allocation determined by central web-based randomization. Randomization will be stratified by gender and the type of central venous catheter (Peripherally Inserted Central Catheter or Hickman/Port-a-Cath/Central line).

Participants will be randomized once the participant has consented and all eligibility criteria have been confirmed.

Randomization will be conducted using a customized web-based program developed for this study. The randomization process will be initiated by the local study coordinator who will access

the web-based system and enter the patient's unique identifier and confirmation of eligibility and informed consent. Specific patient allocation will then be electronically delivered, to the research pharmacy who will prepare and dispense trial medication.

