8.2 DETERMINATION OF SAMPLE SIZE

Using an alpha=0.05, 80% power and event rate estimates of 6.8% in the untreated and 3.7% in the treated population, the estimated sample size would be 860 patients per arm or 1720 patients in total for the full trial. Estimating a 10% lost to follow up this would lead to a required sample of 1892 patients. Enrollment data, event rates, and study drop out will be assessed in this pilot trial will aid in the calculation of the required sample size for the full trial. Due to the low event rates, small differences in the event rates in either patient population will lead to large changes in the sample size required.

For the purposes of the pilot the target sample size is 100 patients with plans to run the pilot trial for 1 year. This would involve 4-6 enrollments/month at the coordinating centre in Ottawa, and 2 enrollments per month at the sites of Halifax and Edmonton.

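### Randomisation is stratified by gender and catheter type, but the full-trial analysis is fixed as an unadjusted Fisher test, which is valid but conservative and ignores the strata

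*Protocol*

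**What the plan says.** Section 4.7 (Randomization) states: "Randomization will be stratified by gender and the type of central venous catheter". The catheter factor has two levels, peripherally inserted lines against all others, so crossing it with gender gives four strata.

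Section 8.1.4 (Full Trial Analyses) states for the primary outcome: "Primary outcome event rates will be compared in the experimental and standard of care arm by an unadjusted" Fisher test, with 95% confidence intervals. For the secondary outcomes it states: "Proportions will be compared between study arms by an unadjusted" Fisher test. Those outcomes are VTE, arterial events, major bleeding, clinically relevant non-major bleeding, other minor bleeding, drug intolerance and death. The protocol contains no stratified or covariate-adjusted analysis.

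Section 8.2 sizes the full trial: "Using an alpha=0.05, 80% power and event rate estimates of 6.8% in the untreated and 3.7% in the treated population", from which "the estimated sample size would be 860 patients per arm".

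Section 4.2 says that clinical data are collected with the methodology of the proposed full trial. If no major design change follows, "the clinical data collected during this trial will be included in the primary and secondary analysis for the full trial".

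**The concern.** Factors important enough to stratify the randomisation would normally enter the primary analysis. If they are prognostic, stratified allocation removes variation that an unadjusted test still counts, so that test becomes somewhat conservative. Here the test is also Fisher's, which is conservative in its own right because it conditions on the total number of events and takes discrete values.

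The protocol does not leave the choice open: it specifies an unadjusted test twice. What is at stake is efficiency and agreement between design and analysis, not false-positive control. Section 4.1 justifies the pilot by the large sample that the full trial needs, and section 8.2 warns how sensitive that number is to the event rates. Power that can be had without extra patients is therefore relevant. Timing matters too. Section 4.2 allows pilot data into the full-trial analysis and the trial is open label, so a change of test is cleanest before those data are seen.

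**Working it through.** **Inputs from the protocol.** Alpha 0.05, power 80%, event rates 6.8% and 3.7%, 860 per arm (8.2); allocation 1:1 and four strata (4.7). Sidedness is not stated. Two-sided is assumed, because one-sided formulas give 640 per arm, or 703 with continuity correction, and do not fit 860.

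**1. Reproducing 860 per arm.** With p1 = 0.068, p2 = 0.037, mean rate p = 0.0525 and d = 0.031, the usual formula is

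n = [1.96·√(2p(1−p)) + 0.8416·√(p1(1−p1) + p2(1−p2))]² / d² = 811.4, so 812 per arm.

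The continuity-corrected version, (n/4)·[1 + √(1 + 4/(n·d))]², gives 875. Exact enumeration of the two-sided Fisher test over all pairs of binomial counts gives:

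| n per arm | Fisher power |
|---|---|
| 850 | 79.6% |
| 857 | 79.9994% |
| 858 | 80.05% |
| 860 | 80.2% |

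So 860 agrees with a calculation for the test that the protocol names.

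**2. Expected events.** 860 × 0.068 = 58.5 and 860 × 0.037 = 31.8, about 90 in total. Large-sample tests are reliable at that count, as step 3 confirms.

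**3. Fisher against the uncorrected Pearson chi-square, no strata, 860 per arm (exact enumeration).**

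| | Fisher | Pearson, uncorrected |
|---|---|---|
| Power, 6.8% vs 3.7% | 80.2% | 82.8% |
| Size, common rate 3.7% | 3.73% | 4.91% |
| Size, common rate 5.25% | 3.93% | 4.97% |
| Size, common rate 6.8% | 4.04% | 4.99% |
| Smallest n per arm for 80% power | 858 | 798 |

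Fisher leaves (5 − 4.04)/5 = 19% to (5 − 3.73)/5 = 25% of the nominal alpha unused. The power difference is 82.83 − 80.16 = 2.7 points, equivalent to 60 patients per arm (60/858 = 7%).

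**4. Adding the strata.** The protocol gives neither stratum sizes nor stratum effects, so these are assumptions. The CMH test was simulated with 400,000 runs per scenario, four strata, 1:1 within each stratum, and overall rates held at 6.8% and 3.7%.

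| Assumed strata | CMH uncorrected, power | Pooled chi-square, power | CMH with correction, power | CMH uncorrected, size at 5.25% |
|---|---|---|---|---|
| Equal sizes, not prognostic | 82.9% | 82.9% | 79.9% | 4.97% |
| Equal sizes, catheter odds ratio 2 | 83.1% | 82.9% | 80.3% | 4.95% |
| Equal sizes, catheter odds ratio 3, gender 1.5 | 83.4% | 83.0% | 80.6% | 4.98% |
| Sizes 10/10/40/40%, odds ratios 1 to 3 | 83.0% | 82.9% | 80.2% | 4.96% |

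A second set of simulations varied the share of peripherally inserted lines from 20% to 80%, the catheter effect from 1- to 3-fold and the sex effect from 1- to 1.3-fold. It gave 82.8% to 83.4% uncorrected and 79.8% to 80.5% corrected. In that set the strata were worth 0 to 0.5 points.

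**5. Losses.** Section 8.2 recruits 1892. After 10% loss, 1892 × 0.9 / 2 = 851 per arm remain. Fisher power is then 79.7% and Pearson 82.4%, so the comparison does not change.

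**The case against.** The strongest reply is that nothing here is an error. Fisher's test controls the type I error at every event rate, and the sample size fits it. The protocol never promises that the strata will be used, so sections 4.7 and 8.1.4 do not contradict each other. All of this stands.

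Preferring an exact test is also defensible. At common event rates between 1.2% and 3%, lower than those planned, the uncorrected chi-square slightly exceeds its nominal level (about 5.05% to 5.14% at 860 per arm). That excess is trivial, and it lies outside the planning range of 3.7% to 6.8%, where the size stays below 5%. It is, though, a good reason to keep Fisher's test for rare outcomes.

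The strata themselves buy little: nothing if they are not prognostic, and about half a point if they are strongly so. A CMH test with continuity correction gives back nearly all the gain. Both points are right. The 83% must not be presented as the benefit of stratifying, and the recommendation depends on using the uncorrected statistic.

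Finally, this concerns a later trial. The pilot's own analyses in 8.1.2 and 8.1.3 are untouched, and it is an inference from section 4.2 that the full trial keeps the same strata. Only about five primary events are expected among 100 pilot patients (50 × 0.068 + 50 × 0.037 = 5.25). This limits the urgency but does not remove the point, because 8.1.4 already fixes the test and 4.2 already provides for the data to be carried forward.

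**Conclusion.** The concern holds, as a matter of efficiency and of matching the analysis to the design. At the planned rates and 860 per arm, the unadjusted Fisher test has 80.2% power and a true size of 3.7% to 4.0%. An uncorrected CMH test stratified by gender and catheter type has about 83% power with size 4.9% to 5.0%. Of the gain of roughly three points, about 2.7 come from leaving Fisher's conservatism behind and 0 to 0.5 from the strata.

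There is no shortfall against section 8.2 and no threat to type I error. The figures assume a two-sided alpha of 0.05, the planned event rates, and a full trial randomised as in section 4.7. The strata component also rests on the stratum sizes and effects assumed above. The change should be made because it costs almost nothing, but the plan would not be invalid without it.

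**What to change.** In section 8.1.4:

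- Make the primary test a CMH test without continuity correction, stratified by gender and catheter type as used at randomisation. Say explicitly that no correction is applied.
- Report the Mantel-Haenszel stratified risk difference with its 95% confidence interval. The section promises intervals but names no effect measure.
- Use the same method for listed secondary outcomes with enough events, for example where the Mantel-Fleiss criterion is met. With 1:1 allocation, t events in total give an expected t/2 in one arm and a possible range of 0 to t, so requiring a margin above 5 on each side means t > 10.
- Keep the unadjusted Fisher test for sparser outcomes and as a sensitivity analysis of the primary outcome.

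The cost is wording, plus one pre-stated rule for choosing the test by event count. The strata are already recorded at randomisation. The 860 per arm can stand as a conservative figure, in which case the benefit is power rather than fewer patients. The wording is best settled before any pilot outcome data are seen by arm.

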2. STUDY SYNOPSIS

Title: A pilot study assessing the feasibility of a randomized controlled trial investigating primary thromboprophylaxis with rivaroxaban in patients with malignancy and central venous catheters (CVC)

Short Title: The TRIM-Line

Protocol Version: 28Feb2018 Version 1.1

Principal Investigators: [name] and [name]

Sponsor: OHRI

Study Centres:

The Ottawa Hospital, General Campus, Ottawa, ON
QEII Health Sciences Centre, Halifax, Nova Scotia
University of Alberta Hospital, Edmonton, Alberta

Timeline: February 2019-September2019

Purpose of Pilot Trial

To determine the feasibility of conducting a multicentre randomized open label-controlled trial evaluating the use of prophylactic dose rivaroxaban to prevent CVC associated venous thromboembolism(VTE) among cancer patients.

Purpose of Full Trial

The purpose of the full trial is to determine the efficacy and safety of prophylactic dose rivaroxaban to prevent CVC associated VTE among cancer patients.

Pilot Trial Endpoints

The primary feasibility outcome for the pilot study is the number of participants recruited per centre per month. We will obtain baseline details of the patient's type, location and treatment of cancer, comorbidities and medications. Secondary feasibility outcomes of the pilot study will include, consent rates, loss to follow up, adherence to therapy defining 80% or greater medication taken as having good adherence to study drug, proportion of screened patients who meet eligibility criteria.

We will document reasons for non-consent in order to assist recruitment for the larger multicentre trial.

Full Trial Endpoints

For the full multicentre trial the outcomes would be as follows: primary outcome symptomatic, radiographically confirmed VTE. Secondary outcomes include major and clinically relevant non-major bleeding (CRNMB), CVC life span, premature CVC removal, CVC lumen occlusion, CVC associated infection and death.

Design

This is a pilot study to be conducted at 3 Canadian Centres. The Ottawa Hospital, QEII Health Science Centre and University of Alberta Hospital. It is an open label randomized controlled trial.

Consenting participants, meeting eligibility criteria will be randomized at the time of enrollment to one of two groups.

Rivaroxaban 10mg po daily x 90 days

OR

Observation

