4.5 WHAT ARE THE MEASURED OUTCOMES FOR THE PILOT STUDY?

The primary feasibility outcome for the pilot study is the number of participants recruited per centre per month. We will obtain baseline details of the patient's type, location and treatment of cancer, and medications. Secondary feasibility outcomes of the pilot study will include, consent rates, loss to follow up, adherence to therapy defining 80% or greater medication taken as having good adherence to study drug, proportion of screened patients who meet eligibility criteria. We will document reasons for non-consent in order to assist recruitment for the larger multicentre trial.

For the full multicentre trial the outcomes would be as follows: primary outcome of symptomatic, radiographically confirmed VTE. Secondary outcomes include major and CRNMB, CVC life span, premature CVC removal, CVC lumen occlusion, CVC associated infection and death.

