4.14 PROPOSED FREQUENCY AND DURATION OF FOLLOW UP

In addition to the initial enrollment visit, patients that are enrolled will receive a telephone follow up at Day-30 +/- 3 days and an in person follow up at Day 90 +/- 3 days.

Post-enrollment follow up visits will include assessment and history for major and minor bleeding, CVC life span, premature CVC removal, CVC lumen occlusion, CVC associated infection and death and assessment of adherence to study drug. Patients will be followed for 90 days +/- 3 days.

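### The full trial's secondary analysis list leaves out four of the seven declared secondary outcomes, all catheter outcomes, and adds two that have no named collection

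*Protocol*

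**What the plan says.** Section 4.5 names the full trial's "primary outcome of symptomatic, radiographically confirmed VTE" and then continues: "Secondary outcomes include major and CRNMB, CVC life span, premature CVC removal, CVC lumen occlusion, CVC associated infection and death". The synopsis gives the same set: "Secondary outcomes include major and clinically relevant non-major bleeding (CRNMB), CVC life span, premature CVC removal, CVC lumen occlusion, CVC associated infection and death".

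Section 4.14 says that the follow-up visits cover "assessment and history for major and minor bleeding, CVC life span, premature CVC removal, CVC lumen occlusion, CVC associated infection and death". The schedule of events collects outcome information at Day 30 and Day 90 by pointing back to section 4.5.

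Section 8.1.4 names one method for the secondary analysis: "Proportions will be compared between study arms by an unadjusted Fisher's test, with 95% confidence intervals reported". It then states which outcomes are to be analysed: "symptomatic VTE, symptomatic ATE, major bleeding, CRNMB, non-major non-CRNMB, medication intolerance/reaction, and all-cause mortality".

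Section 4.2 adds that pilot clinical data go into the full trial's primary and secondary analyses, provided the pilot leads to no major design change that would make them unsuitable.

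**The concern.** The protocol fixes two different sets of secondary outcomes for the same trial. An analyst who follows 8.1.4 would never compare the catheter outcomes between arms, although two sections declare them and a third has them collected. An analyst who follows 4.5 would have to go beyond the list in 8.1.4. A separate analysis plan cannot agree with both, so this is not a detail left for that plan to supply.

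There is also a mismatch in the other direction. Two outcomes that 8.1.4 compares between arms are not named in the sections that say what is collected. This matters during the pilot because pilot patients may later be pooled into the full trial. An outcome captured in only one arm of an open-label study cannot be compared fairly, and the gap cannot be reliably filled afterwards.

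**Working it through.** No arithmetic beyond counting applies, so the check sets the lists side by side. Major bleeding and CRNMB count as two outcomes, as 8.1.4 lists them.

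| Outcome | Declared secondary (synopsis, 4.5) | Named in 4.14 | Listed in 8.1.4 |
|---|---|---|---|
| Major bleeding | yes | yes | yes |
| CRNMB | yes | only as minor bleeding | yes |
| Death | yes | yes | yes |
| CVC life span | yes | yes | **no** |
| Premature CVC removal | yes | yes | **no** |
| CVC lumen occlusion | yes | yes | **no** |
| CVC associated infection | yes | yes | **no** |
| Non-major non-CRNMB bleeding | no | only as minor bleeding | yes |
| Symptomatic ATE | no | **no** | yes |
| Medication intolerance/reaction | no | **no** | yes |
| Symptomatic VTE | no, it is the primary | no, but reached through the schedule's reference to 4.5 | yes |

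**Counts.**
- Seven outcomes are declared, seven are listed in 8.1.4, and three are in both.
- Declared without an analysis: 7 − 3 = 4, which is 4 of 7.
- Listed in 8.1.4 but not declared as secondary: 7 − 3 = 4. One is the primary outcome. Of the other three, minor bleeding is collected under 4.14, which leaves two (ATE and intolerance) with no named collection.

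**Method for catheter life span.** The protocol does not define this outcome. I take it to be the time from insertion, or from randomization, to removal. Section 4.3 follows everyone for 90 days unless they die or withdraw permission for follow-up. Some catheters will still be in place at Day 90, so their full duration is not observed. Some patients may die with the catheter in place, after which removal cannot occur. A test of proportions uses neither the times nor the incomplete follow-up. The other three catheter outcomes can be analysed as proportions, so the method already named would serve them.

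**Route for collecting ATE.** The abbreviation is expanded nowhere in the document; I read it as arterial thromboembolic event. With no mention in 4.5 or 4.14, the remaining route is adverse event reporting. Section 5 starts the reporting period at the first dose of study medication, and section 5.1 defines an adverse event only for someone who has taken at least one dose. Under section 4.8 the standard-of-care arm receives no rivaroxaban. Read literally, the period never opens for that arm.

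**Intolerance/reaction.** The same definition covers suspected drug reactions in the rivaroxaban arm. In the other arm there is no study drug to be intolerant of, so a between-arm test has no clear meaning.

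**The case against.** The strongest reply is that this protocol governs a 100-patient pilot whose primary outcome is recruitment. Sections 8.1.2 and 8.1.3 test no clinical outcome between arms, pooling is conditional, and the full trial's analysis can still be settled before that trial starts. This stands, and it limits the consequence to the full trial. It does not remove the contradiction, because the protocol chose to state the full-trial analysis and did so in two incompatible ways.

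On ATE, it can be said that section 5.2 has every participant questioned about adverse events and that the schedule's adverse event row carries no arm label. That suggests an intention to collect in both arms. However, the schedule's compliance row carries no arm label either and can apply only to the treated arm. The definition and the reporting period are explicit, so the text needs repair whatever was intended.

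A reader might also infer four stronger points that the document does not support:
- **That 8.1.4 misapplies Fisher's test to catheter life span.** It does not, because that outcome is missing from its list. The accurate statement is that the outcome has no analysis and the only method named would not suit it.
- **That the additions are unplanned tests.** Section 4.5 introduces its list with the word *include*, which allows additions, and 8.1.4 names them in advance. The objection to ATE and intolerance concerns collection.
- **That listing VTE again creates a second test of the primary.** The population, the sensitivity analysis and the test are the same in both places, so no result changes. This is editorial.
- **That pilot data on the catheter outcomes are being lost.** They are collected under 4.14 and through the schedule.

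**Conclusion.** The concern holds in this form. Four of the seven declared secondary outcomes of the full trial have no analysis in 8.1.4, and one of them, catheter life span, could not be analysed properly by the only method named. Two outcomes in 8.1.4, ATE and intolerance/reaction, have no named collection in 4.5 or 4.14. As written, ATE has no defined capture route in the untreated arm.

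The reach is limited. The primary analysis is unaffected. So is the sample size of 860 per arm, which rests on the event rates of 6.8% and 3.7% set out in section 8.2. The pilot's feasibility analyses do not use any of these outcomes.

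The conclusion on life span assumes that it means a time to removal. The conclusion on ATE rests on a literal reading of sections 5 and 5.1. The omission of the four catheter outcomes needs neither assumption.

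**What to change.** 1. Use one list of full-trial secondary outcomes in the synopsis, 4.5, 4.14 and 8.1.4.
2. Add the four catheter outcomes to 8.1.4. Compare premature removal, lumen occlusion and infection as proportions. Analyse catheter life span as time to removal, censored at the end of follow-up, with death handled as a competing event. State whether time runs from insertion or from randomization, since insertion may precede enrolment by up to 72 hours.
3. Define ATE. Then either add ATE and intolerance/reaction to 4.5 and 4.14, with ATE collected in both arms, or drop them from the between-arm comparison. If ATE is to rely on adverse event reporting, the definition and reporting period in section 5 must also cover the standard-of-care arm, for example by starting at randomization.
4. Keep VTE under the primary analysis only. If 8.1.4 means something other than the radiographically confirmed endpoint, define the difference.

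The cost is wording and a little more analysis. The catheter data are already planned at both follow-up contacts. The only new collection would be ATE and, if kept, intolerance. That part is best settled before pilot patients who may be pooled have been followed up.

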3.5 WHY IS AN OPEN-LABEL TRIAL DESIGN CHOSEN?

The current standard of care in most cancer patients is to not use outpatient thromboprophylaxis. Patients often receive thromboprophylaxis only when admitted to hospital or subject to additional risks. Not using a placebo tablet reduces study expense and complexity while improving patient acceptance and potentially enrollment into the trial. Since the primary endpoints in the larger planned multicentre study are objective, imaging confirmed thrombosis and bleeding outcomes and not expected to be adversely affected with an open label design.

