4.8 TREATMENT ARMS

Treatment Arm 1: Experimental

Rivaroxaban 10 mg po daily for 90 (+/-3) days. After the Day 90 follow up, the study treatment will be discontinued, and subsequent treatment will be at the discretion of the attending physician.

Treatment Arm 2: Standard of care

No rivaroxaban prophylaxis. Management will be at the discretion of the attending physician.

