4.10 PRODUCT LABELLING

Rivaroxaban will be purchased through the research pharmacy and relabeled for this trial according to the template below. Each participant in the treatment arm will be given a 93-day supply of study drug (according to the randomization scheme) at Day 1.

Product information for each of the study medications is listed in Appendix 4.

Rivaroxaban 10 mg Expiration: DD-MMM-YYYY Store at room temperature between +15°C and +25°C Lot # ----- Protocol : TRIM-Line Trial Sponsor: The Ottawa Hospital Research Institute, [name] Investigational drug -- to be used only by a qualified Investigator	Rivaroxaban 10 mg Expiration: JJ-MM-AAAA Conserver à l'air ambiant, entre +15°C et +25°C, Lot # ----- Nom du Protocole: TRIM-Line Trial Commanditaire: Institut de recherche de l'Hôpital d'Ottawa [name] Médicament expérimental -- à être utilisé seulement par un Investigateur qualifié
--	---

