- **Expected (anticipated):** the event is identified in nature, severity, or frequency in the investigator brochure, product monograph or in the protocol.
- **Unexpected (unanticipated):** the event is not identified in nature, severity, or frequency in the investigator brochure, the product monograph or in the protocol.

CANCER RELATED AES

For this study, adverse events that are possibly related or related to cancer and its treatment will not be recorded as an adverse event. However, if the cancer related event meets the criteria of a SAE, the event will be recorded and reported accordingly regardless of the causality. These include but are not limited to:

- Nausea
- Vomiting
- Changes in bowel function – including constipation, diarrhea, bloating or flatulence
- Abnormal white blood cell count
- Urinary symptoms
- Appetite changes
- Fatigue or lethargy
- Hair loss
- Mouth or throat changes
- Weight loss
- Confusion or altered level of consciousness
- Progression of cancer

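### Section 8.1.4 tests medication intolerance/reaction between arms, although the control arm takes no study drug or placebo and the adverse event rules record such events only after a first dose

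*Protocol*

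**What the plan says.** Section 8.1.4 sets the method for the full trial's secondary outcomes: "Proportions will be compared between study arms by an unadjusted Fisher's test, with 95% confidence intervals reported". The outcomes are "symptomatic VTE, symptomatic ATE, major bleeding, CRNMB, non-major non-CRNMB, medication intolerance/reaction, and all-cause mortality". The analysis is by intention to treat, and "Intention to treat analysis will be supplemented by a sensitivity analysis that excludes subjects who did not complete the allocated treatment plan".

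The control arm is described in section 4.8: "No rivaroxaban prophylaxis. Management will be at the discretion of the attending physician". Section 3.5 explains why there is no placebo: "Not using a placebo tablet reduces study expense and complexity while improving patient acceptance and potentially enrollment into the trial". Section 4.10 supplies drug to one arm only: "Each participant in the treatment arm will be given a 93-day supply of study drug".

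On recording, section 5.1 makes at least one dose of study medication part of the definition of an adverse event, and section 5 opens the reporting period at the first dose. Medication intolerance/reaction is not defined anywhere in the protocol. It is not among the full-trial outcomes in section 4.5, nor among the follow-up assessments in section 4.14.

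**The concern.** A between-arm test of proportions is informative when participants in both arms can have the event and the event is looked for in the same way in both. The protocol does not secure this for medication intolerance/reaction. One arm takes the study drug, the other takes nothing in its place, and the adverse event rules follow the drug.

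A significant p-value could then be read as evidence of comparative harm and a non-significant one as evidence of good tolerability, and neither would follow from the test. The quantity of interest is how often people who take rivaroxaban do not tolerate it. Neither planned analysis set gives that directly. Intention to treat counts participants who never start the drug, and the sensitivity analysis tends to remove those who stopped because of intolerance.

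**Working it through.** **Inputs.** Section 8.2 gives 860 per arm (1720 in total), or 1892 with its allowance for loss, which is 1892/2 = 946 per arm. It also gives alpha = 0.05. Section 4.7 gives 1:1 allocation. The protocol gives no rate for medication intolerance/reaction, so the rates used below are assumptions.

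**The plan's own figure.** The usual two-proportion formula for 6.8% against 3.7%, two-sided 0.05 and 80% power, gives 812 per arm, or 875 with a continuity correction. The stated 860 is within 2% of the latter and is taken as given here.

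**Reading 1: reaction to study drug.** Without crossover the control count is zero by design. For k events against 0 with n per arm, the two-sided Fisher p-value is

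p = 2 × C(n, k) / C(2n, k), which is close to 2 × (1/2)^k when n is large.

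- k = 5, n = 860: 2 × 0.03107 = 0.062.
- k = 6, n = 860: 2 × 0.01549 = 0.031.
- k = 8, n = 860: 0.008.
- n = 946: 0.062 for k = 5 and 0.031 for k = 6.
- n = 50 (half the pilot's 100): 0.056 for k = 5 and 0.027 for k = 6.

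The threshold is therefore 6 events whatever the trial's size, which at 860 is 6/860 = 0.70%. The chance of reaching it is P(X ≥ 6) with X ~ Binomial(n, r), where r is the assumed rate on rivaroxaban:

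| Assumed r | 860 per arm | 946 per arm |
|---|---|---|
| 0.5% | 26% | 34% |
| 1% | 86% | 91% |
| 2% | more than 99.9% | more than 99.9% |

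The direction is set by design. Significance is not: it depends on the rivaroxaban count.

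**Reading 2: reaction to any medication.** Control participants can have such a reaction. The question is whether it would be recorded, and the relevant places line up as follows.

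- Section 5.1: an adverse event needs at least one dose of study medication.
- Section 5: the reporting period starts at the first dose, so for an undosed control participant it never opens.
- Synopsis schedule: there is a separate row for outcome information, but it refers to section 4.5, which does not list this outcome.
- Section 4.14: the follow-up assessments do not list it either.

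No other route of collection is described, so as written the outcome is recordable in one arm.

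**Denominator.** If a fraction s of the rivaroxaban arm starts the drug and the rate among starters is r, intention to treat reports s × r. With an assumed s of 0.90 and r of 1%, it reports 0.90 × 1% = 0.9%. The gap is modest, but it always runs downwards.

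**What an interval would say.** For 6 events among 860 dosed participants, the Wilson 95% limits are [(6 + 1.92) ± 1.96 × √(6 × 0.993 + 0.96)] / (860 + 3.84) = (7.92 ± 5.16) / 863.84, that is 0.32% to 1.51%. For 5 events the same formula gives 0.25% to 1.35%. The two results describe nearly the same tolerability, yet their p-values fall on opposite sides of 0.05.

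**The case against.** The strongest reply is that the protocol never limits the term to rivaroxaban. Control participants have cancer, are managed as their physician sees fit, may take antiplatelet agents or NSAIDs (section 4.13), and may cross over (section 8.1.3 counts this). A reader might infer that the control arm cannot have the event at all. The documents do not support that, because it requires a definition the protocol does not give.

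Two other strong readings also fail. A reader might say the result is fixed in advance, but only the direction is, and only under the study-drug reading. A reader might say the analysis tells us nothing about harm. That goes too far: section 8.1.4 asks for 95% confidence intervals, the rivaroxaban-arm proportion still describes tolerability, and bleeding and mortality are compared separately in the same list.

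Nor does the rule on cancer-related events in section 5.1, "adverse events that are possibly related or related to cancer and its treatment will not be recorded as an adverse event", show one-sided recording. It draws no distinction between arms and would lower counts in both. The one-sidedness comes from the first-dose condition alone.

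It can also be said that section 5.2 has every participant questioned about adverse events at each visit, and that the schedule does not confine its adverse event row to the treatment arm. Some sites might therefore record control events despite the definition. That would not restore the comparison, since the control count would depend on which part of the protocol a site followed.

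Finally, the stakes are low. The analysis belongs to a later trial and no sample size rests on this outcome. That stands, and it limits the severity.

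**Conclusion.** The point holds as a minor one. Section 8.1.4 fixes a between-arm Fisher's test for an outcome to which one arm is either not exposed, apart from crossover, or for which it has no recording route. Under the study-drug reading the test asks whether the rivaroxaban rate exceeds about zero, and 6 events in 860 (0.70%) are enough for p < 0.05. Under the any-medication reading the p-value mixes drug effect with one-sided ascertainment. In neither case does it measure comparative harm.

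The Fisher figures rest on a control count of exactly zero, so no crossover events. The probabilities of significance rest on assumed rates of 0.5% to 2%. The ascertainment argument rests on sections 5 and 5.1 being followed as written.

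The pilot's recruitment, consent, retention and crossover estimates (sections 8.1.2 and 8.1.3) are untouched. There is still a reason to settle the matter now: section 4.2 intends to carry pilot clinical data into the full trial if the design does not change materially, and events not recorded in control participants during the pilot may be hard to recover later.

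**What to change.** Remove medication intolerance/reaction from the between-arm Fisher list in section 8.1.4. Define it as intolerance of or reaction to study drug, and report it for the rivaroxaban arm only, as a proportion of participants who took at least one dose, with a Wilson 95% interval. Section 8.1.3 already uses that method. Keep the between-arm comparisons for VTE, ATE, the bleeding categories and all-cause mortality.

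If a reaction to any medication was intended, say so, add the outcome to sections 4.5 and 4.14, and record it in the same way in both arms from randomization. A between-arm comparison would then be legitimate.

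The first option costs a sentence or two in section 8.1.4 and the loss of a p-value for intolerance, with no new patients or data. The second costs some extra recording in the control arm.
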